A factor which may facilitate such stimulus-controlled smoking routines in PSZ is that smokers with schizophrenia (SmoSz) appear remarkably insensitive to subjective effects of nicotine. According to theories of drug dependence, drug effects insensitivity would facilitate a habitual, cue-locked drug taking mode.

Furthermore, automatized drug-taking is reportedly associated with frontoexecutive control deficits, a hallmark of the neurocognitive profile of schizophrenia. Thus, nicotine insensitivity and cognitive control deficits may facilitate automatized, stimulus-driven smoking in SmoSz.

The overall aim of this proposal is to determine whether tobacco smoking in PSZ is under disproportionately strong cue control, and to test whether insensitivity to the subjective effects of nicotine and/or cognitive control deficits can account for this.

Aim 1 is to test whether tobacco smoking behavior is under greater cue control in SmoSz than in matched healthy control smokers (SmoCon). Approach: Indices of cue-controlled smoking are obtained by quantifying the degree to which virtually nicotine-free cigarettes can maintain smoking behavior over eight hours under standardized laboratory conditions, in the presence of transdermal nicotine replacement. Nicotine-free cigarettes evoke a near-complete set of internal and external stimuli and behavioral routines associated with tobacco smoking, but without ensuing nicotine delivery, thus capturing the essence of stimulus control over smoking behavior.

Aim 2 is to test whether SmoSz are less sensitive to the subjective effects of nicotine than SmoCon. Approach: In a standardized laboratory paradigm, SmoSz and SmoCon discriminate research cigarettes of differing nicotine yields, and report on subjective state measures after each cigarette.

Aim 3 is to determine whether nicotine insensitivity is related to cue-control over smoking behavior, and can account for the group difference therein.

Aim 4 is to determine whether cognitive control deficits are related to cue-control over smoking behavior, and can account for the group difference therein. Approach: A cognitive control index will be derived from tasks selected from the RDoC matrix.

2 * Discuss the research design including but not limited to such issues as: probability of group assignment, potential for subject to be randomized to placebo group, use of control subjects, etc.:

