Participants are instructed not to smoke or ingest any nicotine from waking up until session start at ~9 am, verified by expired CO \leq 7 ppm. If this threshold is exceeded, the session may be rescheduled. Participants first complete the MTWS, AWS, & QSU (see above). The nicotine discrimination procedure is then started. Participants are informed that their task is to compare different types of cigarettes, and that nicotine content is one of the parameters in which these cigarettes may differ. On each trial, participants take four 2-s puffs via the Clinical Research Support System (CReSS) portable device, to standardize smoking topography, with 30 s between puffs (71-74). Puff duration and inter-puff interval is timed by visual cues on an instruction screen. The CReSS time-stamps puff onset and duration. Trials are separated by 20 min no smoking.

The first 2 trials are reference trials, over which participants take 4 puffs on the Very Low Nicotine Content (VLNC) and the 0.8 mg-yield cigarette each, with sequence counterbalanced across participants. The two cigarettes are identified by letter code (A and B, counterbalanced). Four discrimination trials follow, in which the participant is blind with regards to cigarette identity. The sequence in which the two cigarette types are sampled (ABBA, BAAB, ABAB, BABA) is counterbalanced and double-blind, i.e., only the statistician and dispensing pharmacist know the sequence. After each discrimination trial, participants choose whether the sampled cigarette was of type A or B, complete the MTWS, AWS, QSU, and mCEQ, and indicate on a scale from 1 to 5 how much they want to smoke a cigarette like this, and how satisfying and how strong they thought the cigarette was. After the 4th discrimination trial, participants have a break and a light lunch, staying on the premises to ensure continued smoking abstinence. They then receive another reference trial with the VLNC and 0.8-mg cigarette each, and complete another 4 discrimination trials as described above.

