Some participants may already have done a SCID in the context of clinical care or another study. If this SCID was done at the MPRC, it will not be redone. The diagnostic information will have entered clinical records and will be accessed under a partial HIPAA privacy waiver.

3 * Describe the duration of an individual participant's participation in the study:

The shortest time within which the study can be completed by any participant is 1 week. A maximum of 3 months may expire between any of the four sessions described above (although efforts will be made to not exceed 2 weeks). Thus, the maximum completion time is 9 months.

4 * Describe the amount of time it will take to complete the entire study:

The is a two-year study.

5 * Describe any additional participant requirements:

None.

ID: VIEW4E0280585B400
Name: v2_Study Procedures

Sample Size and Data Analysis

If you uploaded a separate research protocol document in the 'Research Protocol' page, cite the applicable section and page numbers from that document in the answer boxes below.

1 * Provide the rationale and sample size calculations for the proposed target population:

Power analyses indicate that, at $\beta=0.8$, $N=45$ per diagnostic group would enable detection of medium effect sizes (Cohen's $d=0.6$, Cohen's $f=0.3$) with the analyses described below. To prepare for a 20% attrition rate, we will randomize 112 participants for 90 completers. Based on an expected 20% screening failures, we anticipate that screening 140 volunteers will result in 112 enrollments, but to be on the safe side, we set the enrollment ceiling at 160.

2 * Provide the plan for data analysis. Include in the description the types of comparisons that are planned (e.g., comparison of means, comparison of proportions, regressions, analysis of variance, etc.), which is the primary comparison/analysis, and how the analyses proposed will relate to the primary purposes of the study:

- Hypothesis 1 (smoking is under greater cue control in SmoSz than SmoCon) is tested by two-sample t-test comparing groups on breath CO after 8 hrs of ad libitum VLNCcig smoking (ANCOVA if group matching is suboptimal for 1 or more variables). Secondary analysis: ANOVA (or ANCOVA) to compare groups on the number of VLNCcigs smoked in the first vs. last 2 hrs of the Ad Lib Smoking Session (group x time point).

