- Hypothesis 2 (SmoSz are less sensitive to subjective nicotine effects than SmoCon) is tested by two-sample t-test (or ANCOVA) comparing nicotine discrimination accuracy between groups. Secondary analysis: The composite subjective state score after smoking a VLNC or a 0.8 mg-yield cigarette is compared between SmoSz and SmoCon by ANOVA (group x cigarette type), or ANCOVA if indicated (see above).

- Hypothesis 3 (nicotine sensitivity is related to cue control and can account for the group difference therein): Regression analysis tests the impact of discrimination accuracy on cue control while controlling for the group effect. To evaluate the degree to which nicotine insensitivity can statistically account for the group difference in cue-control, we measure the reduction in the group effect when entering discrimination accuracy, with a >25% reduction in β group defined as significant. To determine the percentage of between-group variance in cue control statistically accounted for by nicotine sensitivity, we quantify the reduction in variance explained by the group factor when including discrimination accuracy as a covariate in ANCOVA.

- Hypothesis 4 (cognitive control deficits can account for cue-control and for the group difference therein) is tested in a manner analogous to Hypothesis 3.

ID: VIEW4E02806052800
Name: v2_Sample Size and Data Analysis

Sharing of Results

1 * Describe whether results (study results or individual subject results, such as results of investigational diagnostic tests, genetic tests, or incidental findings) will be shared with subjects or others (e.g., the subject's primary care physicians) and if so, describe how it will be shared:

If significant abnormalities are identified during screening, these test results would be given to the subject, together with a recommendation regarding the appropriate type of follow-up (e.g., see family doctor or specialist). With written authorization from the participant, test results may also be shared with their care provider.

The overall trial outcome would not be shared with individual participants or their providers but will be made accessible via scientific publication.

ID: VIEW4E02808CBD800
Name: v2_Sharing of Results

Research with Drugs or Biologics

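### Hypotheses 3 and 4: a drop of more than 25% in the group coefficient is called significant without a standard error, interval or alpha, so the claim has no fixed false-positive rate

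*Combined protocol and SAP*

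**What the plan says.** All of this is in the combined protocol and SAP.

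- **Overall aim** (Justification, Objective, & Research Design, item 1): having asked whether smoking in schizophrenia is under stronger cue control, the study sets out "to test whether insensitivity to the subjective effects of nicotine and/or cognitive control deficits can account for this".
- **Hypothesis 1** (Sample Size and Data Analysis, item 2): a two-sample t-test, or ANCOVA, compares the groups on breath CO after the ad libitum session.
- **Hypothesis 2**: it "is tested by two-sample t-test (or ANCOVA) comparing nicotine discrimination accuracy between groups".
- **Hypothesis 3**: first, "Regression analysis tests the impact of discrimination accuracy on cue control while controlling for the group effect". Then "we measure the reduction in the group effect when entering discrimination accuracy, with a >25% reduction in β group defined as significant". The next sentence adds a share of between-group variance, with no threshold.
- **Hypothesis 4**: it "is tested in a manner analogous to Hypothesis 3". Its mediator is introduced under Aim 4: "A cognitive control index will be derived from tasks selected from the RDoC matrix". Item 2 lists no group comparison of that index.
- **Power** (item 1): 45 per group "would enable detection of medium effect sizes (Cohen's $d=0.6$, Cohen's $f=0.3$) with the analyses described below".

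No alpha is stated in either item.

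**The concern.** Whether the groups differ less once a mediator is entered is a question about an indirect effect, and that estimate has sampling error. A fixed cut on the ratio of two coefficients ignores the error, so its false-positive rate moves with the size of the group effect, the group difference in the mediator and the mediator-outcome correlation. None of these is known in advance. The ratio is least stable when the group effect in the denominator is small, and nothing stops the rule being applied when Hypothesis 1 has failed.

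For Hypothesis 3 the plan already holds both path tests: Hypothesis 2 (group to accuracy) and the adjusted regression (accuracy to cue control). It does not say that the mediation claim depends on them. For Hypothesis 4 the group-to-mediator test is absent.

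At stake is a published statement that nicotine insensitivity or poor cognitive control significantly accounts for the group difference, made at an error rate nobody has set. That statement is half of the overall aim.

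**Working it through.** **1. The plan's own figure.** Two-sided alpha of 0.05 is assumed, because none is stated; the stated β=0.8 is read as power.

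- Two-sample t-test, d=0.6, 45 per group: noncentrality 0.6 × √(45/2) = 2.85, power 0.804.
- F test for one regressor, f=0.3, N=90, df 1 and 87: noncentrality 0.3² × 90 = 8.1, power 0.804.

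The 0.8 therefore reproduces for the two-group tests and for the single mediator regression.

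**2. What the rule compares.** Let ĉ be the unadjusted group effect, â the group difference in the mediator and b̂ the mediator coefficient adjusted for group. In least squares the drop in the group coefficient equals â·b̂, so the rule is â·b̂/ĉ > 0.25. There is no mediation if a=0 or b=0.

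**3. Hand check with b=0.** With within-group SDs of 1, Var(â) = Var(ĉ) = 2/45 = 0.0444 and Var(b̂) ≈ 1/86. Taking ĉ as positive, the rule fires when â·b̂ − 0.25ĉ > 0. At a CO effect of 0.6 this quantity has mean −0.15 and variance a²/86 + 0.0444/86 + 0.0625 × 0.0444.

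- a=0.6: 0.0042 + 0.0005 + 0.0028 = 0.0075; SD 0.0865; z = 1.73; about 4%.
- a=1.2: 0.0167 + 0.0005 + 0.0028 = 0.0200; SD 0.1416; z = 1.06; about 14%.

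**4. Simulation with no mediation.** Mediator = a·group + N(0,1). CO = (total − a·b)·group + b·mediator + error, with within-group SD of CO equal to 1. There are 45 per group, two-sided 5% tests and 100,000 runs per case. Total d=0.6 is the plan's figure. The smaller totals, a=1.2 and the correlations 0.3 and 0.5 are assumptions, because the documents give no path sizes. Each cell lists false-positive rates (%) for a true CO effect of 0.6 / 0.4 / 0.3 / 0.

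| Case | Rule as written | Rule + H1 | H1 + both paths + direction |
|---|---|---|---|
| a=0.6, b=0 | 4.1 / 11.0 / 16.0 / 26.9 | 1.5 / 1.3 / 0.9 / 0.2 | 1.6 / 0.9 / 0.6 / 0.1 |
| a=1.2, b=0 | 13.8 / 22.8 / 27.8 / 37.2 | 8.4 / 6.2 / 4.1 / 0.9 | 2.1 / 1.2 / 0.7 / 0.1 |
| a=0, r=0.3 | 2.2 / 8.5 / 15.1 / 32.4 | 1.0 / 1.4 / 1.3 / 0.6 | 1.8 / 1.4 / 1.1 / 0.4 |
| a=0, r=0.5 | 5.6 / 15.5 / 24.7 / 49.1 | 4.3 / 6.2 / 5.7 / 2.3 | 2.5 / 2.2 / 1.9 / 0.9 |

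The first two entries in the top cell of each b=0 row agree with step 3. Replacing the two path tests by a percentile bootstrap interval for the indirect effect (1,000 resamples, 4,000 runs per case), with H1 and direction still required, gives a worst case of 3.0%.

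**5. Power with all paths medium.** f=0.3 gives r² = 0.09/1.09 = 0.083, so b=0.287. With a=0.6 and total 0.6, the true reduction is 0.6 × 0.287/0.6 = 28.7%.

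| Criterion | Worst of 16 cases (%) | Power |
|---|---|---|
| Rule as written | 49.1 | 0.57 |
| Rule + H1 | 8.4 | 0.41 |
| Rule + H1 + regression | 6.2 | 0.39 |
| H1 + both paths + direction | 2.5 | 0.52 |
| H1 + bootstrap interval + direction | 3.0 | 0.52 |
| H1 + both paths + 25% minimum | 2.0 | 0.38 |

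Both paths without H1 have power 0.63. No version reaches the stated 0.8.

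**6. Coarseness of accuracy.** Under Study Procedures, accuracy rests on four binary trials, after which participants "complete another 4 discrimination trials as described above". Treating it as the share correct over eight trials, with an assumed control accuracy of 0.79, changes no false-positive rate by more than about 0.6 percentage points.

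**The case against.** The best defence is that the sentence describes magnitude. It opens by speaking of degree, it follows an inferential regression, and 25% may be meant as the smallest reduction worth mentioning. Hypothesis 3 also presupposes a group difference and an association, so a sensible analyst would look at Hypothesis 1 and the regression first. On that reading the worst case is 6.2%, and adding the group-to-mediator test makes it 2.0%. At the planned d=0.6, three of the four no-mediation cases lie at 2-6% even without conditions. The 27-49% rates arise only when there is no CO difference to explain. In the 16-25% cases, 60-77% of the false positives come with a non-significant Hypothesis 1 (1 − 6.2/15.5 and 1 − 5.7/24.7).

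For Hypothesis 4, the background and task descriptions treat impaired cognitive control in schizophrenia as established, so equal groups on that mediator are unlikely. The relevant case is then a large group difference with no association. There the 14% at planned size falls to 2.4% once the regression is required.

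Finally, the 25% rule and the two-path test answer different questions. A 25% cut should fire about half the time when the truth is near 25% (about 47% at exactly 25%).

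Much of this stands, and it limits the size of the problem. It does not remove it. The text calls the cut-off significant and states none of these conditions. The regression alone is not enough for Hypothesis 3, where the group difference in accuracy is itself in question. Rule plus regression without Hypothesis 1 still reaches 25% at a CO effect of d=0.3 and 49% at d=0. If 25% is a relevance threshold, it should be labelled as one.

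**Conclusion.** The concern holds and should be fixed. The rule has no set error rate: about 4% at the plan's effect sizes, 2-28% over CO effects of d=0.3-0.6, and higher only if the groups do not differ on CO. Requiring Hypothesis 1 still leaves up to 8.4%. Linking the claim to Hypothesis 1, both paths and direction gives at most 2.5% over the same cases and, with Hypothesis 1 required in both, more power (0.52 against 0.41). The power gain partly reflects that the two-path test asks for a non-zero rather than a 25% reduction.

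The exact rates rest on normal data, two-sided 5% tests and assumed path sizes. The conclusion that the rate is not fixed does not depend on those choices. Hypothesis 1, the test of the main outcome, is not affected.

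**What to change.** In Sample Size and Data Analysis, item 2:

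- Stop defining the 25% reduction as significant. Report the percentage reduction as a description with a bootstrap confidence interval.
- State that a mediator statistically accounts for part of the group difference only if Hypothesis 1 is significant, the groups differ significantly on the mediator, the adjusted mediator regression is significant, and the indirect effect has the direction of the group effect. A 95% bootstrap interval for the indirect effect that excludes 0 may replace the two path tests.
- For Hypothesis 4, add the group comparison on the cognitive control index.
- If a minimum size is wanted, keep 25% as an added condition, labelled as such, and state its power (0.38 with all paths medium).
- State the alpha and sidedness of these tests.

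In item 1, limit the 0.8 power to the two-group tests and the single mediator regression. State that, with all paths medium, the mediation claim has power of about 0.63 on both paths alone, or about 0.52 with Hypothesis 1 also required.

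The cost is a linking sentence, one extra comparison and wording in two items, with no new data. The stated power for this part becomes less favourable. Without the 25% minimum a small non-zero indirect effect can qualify, so the percentage reduction and its interval should always be reported beside the claim.

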5.1 If Yes, what procedures are in place to assure safety?

Interviews

You indicated that this study involves key informant or semi-structured individual interviews.

1 * Are any of the questions likely to cause discomfort in participants or cause harm if their confidentiality were breached? (i.e., Illegal activities)

Yes No

2 * Upload a copy of the interview script or guide that will be used to guide the interviews:

Name	Created	Modified Date
Structured Clinical Interview for DSM(0.01)	6/14/2019 3:43 PM	6/14/2019 3:43 PM
Evaluation to sign consent(0.01)	6/14/2019 3:42 PM	6/14/2019 3:42 PM

3 * What is the individual duration of each interview and what is the entire duration of the interviews?

Evaluation to Sign Consent: ~3 min

Structured Clinical Interview for DSM: 25-60 min, depending on answers

4 * How will the interview responses be recorded and by whom?

The responses will be recorded by the rater, a clinical research assistant at the MPRC, on assessment forms (attached) labeled by subject ID code, date, study number and rater ID. The data are then entered into a secure database.

5 * Do any questions elicit information related to the potential for harm to self or others?

Yes No

5.1 If Yes, what procedures are in place to assure safety?

If a participant were to disclose his or her intent to harm him- or herself or others, the participant will be escorted to a psychiatrist, to a social worker, or to another clinician at the MPRC for an immediate evaluation. These clinicians will then determine appropriate action and follow-up depending on the circumstances.

ID: VIEW4E0947A633C00
Name: v2_Interviews

Observation

You indicated that this study involves individual or group behavioral observations.

1 * Please describe what is being observed.

Ad libitum smoking of very low nicotine content cigarettes (VLNCcigs) for 8 hours at the MPRC while wearing a nicotine patch. Participants spend their time in a day room and walk to a smoking room whenever they wish to smoke VLNCcigs. The number of smoked cigarettes is recorded, and participants exhale into a CO breathalyzer (see Study Procedures for details).

2 * Are any of the observations likely to cause harm if confidentiality were breached? (i.e., Illegal activities)

Yes No

3 * How will individuals identities be protected?

All outcome measures are recorded on forms labeled with only subject ID code, study number, date, and subject and rater initials. No video or audio recordings are taken.

4 * How will observations be recorded?

On paper forms not containing the subject's name or other PII.

ID: VIEW4E0BBF1EF0400
Name: v2_Observation

Testing

You indicated that this study involves neuropsychological or psychophysiological testing.

If you uploaded a separate research protocol document in the 'Research Protocol' page, cite the applicable section and page numbers from that document in the answer boxes below.

- 1 * List all of the tests to be used in the study, including both standardized and non-standardized assessments:
 - Two computerized tasks will be performed:
 1. ExpectancyAX-CPT
 2. Stroop paradigm
 - 3. The WASI Vocabulary and Matrix Reasoning subtests to assess intellectual competence
 - 4. The Reasoning/Problem Solving subscale of the MATRICS Consensus Cognitive Battery (MCCB)
 - 5. Wechsler Test for Adult Reading (WTAR)
- 2 * Describe procedures related to all testing:
 - Computerized ExpectancyAX-CPT: Atrial consists of the letters A or B (contextual cue) followed by an X or Y. The default after each letter is a non-target response; only an X that was preceded by an A requires a target response. After the Acue, there is an 80% chance that an X will follow.
 - Computerized Stroop paradigm: Color-words are presented, and subjects say aloud, as quickly as possible, the color in which the word is written. For congruent trials, the color-word is presented in a matching color (e.g. RED in red), for incongruent trials in a non-matching color (e.g. RED in blue).
 - The WASI subtests are paper and pencil tests and will be administered by an investigator during one of the first three visits (screening, nicotine exposure session prior to lozenge administration, or first outcome measurement session). The setting is a private room, seated at a table.
 - The MCCB reasoning/problem solving domain is tested by a series of mazes, completed as paper & pencil tests, of varying difficulty.
 - The WTAR consists of a list of words of varying difficulty which the participant is asked to read out loud.

- 3 * Upload relevant testing materials:

Name	Created	Modified Date
MCCB Reasoning/Problem solving (Mazes)(0.01)	6/14/2019 4:13 PM	6/14/2019 4:13 PM
Wechsler Test of Adult Reading(0.01)	6/14/2019 4:05 PM	6/14/2019 4:05 PM
WASI Vocabulary subtest(0.01)	6/14/2019 3:58 PM	6/14/2019 3:58 PM
WASI Matrix Reasoning(0.01)	6/14/2019 3:57 PM	6/14/2019 3:57 PM

- 4 * What is the individual duration of each test and what is the entire duration of all tests?

- ExpectancyAX-CPT: ~30 min
- Stroop task: ~ 30 min
- WASI subtests: 15-30 min
- MCCB reasoning/problem solving: ~10 min
- WTAR: 5 min

- 5 * Are any of the questions likely to cause discomfort in participants or cause harm if their confidentiality were breached? (i.e., Illegal activities)

Yes No

- 6 * Do any questions elicit information related to the potential for harm to self or others?

Yes No

- 6.1 If Yes, what procedures are in place to assure safety?

ID: VIEW4E0BC1E3C2800
Name: v2_Testing

Deception

You indicated that this study involves deception.

- 1 * Indicate why deception is the only feasible means of conducting the research. Include information about the likely characteristics and cultural values of the participants that contribute to the justification for using deception:
Tobacco smokers tend to have firm beliefs about the role of nicotine for the effects of tobacco smoking and their smoking.
- 2 * Describe the manner in which the participants are being deceived. Specify the information that will be withheld from the participants or the misinformation that will be provided to them:
Participants will be informed that the research cigarettes they will be smoking as part of this study may differ from each other and from conventional cigarettes in different tobacco constituents including tar, nicotine, and carbon monoxide, when in fact the only difference is in nicotine content. Furthermore, participants will be informed that the skin patch they receive in the Ad Libitum Smoking Session may or may not contain nicotine, when in fact it always contains nicotine.
- 3 * Provide the rationale/justification for the deception:
Smokers will be asked to self-report on their subjective state after comparing cigarettes of different nicotine content. For valid research results, they must not focus on expected effects of nicotine but report their subjective state in an unbiased manner. Furthermore, we measure to what degree smoking is maintained by virtually nicotine-free cigarettes in the presence of nicotine replacement, as a measure of cue-controlled smoking. Knowledge that the cigarettes are nicotine-free and that the patch contains nicotine would most likely alter (reduce) smoking behavior based on the conception that smoking is nicotine-seeking.
- 4 * Will confederates be used?
 Yes No
- 5 * Detail the elements of deception that are incorporated into the informed consent process and document:
The study title is "Cigarette Smoking in Smokers With and Without a Diagnosis of Schizophrenia", not "Nicotine Insensitivity and Cue-Controlled Smoking in People with Schizophrenia", the title of the grant application, which would give away the focus on the presence vs. absence of nicotine effects. Furthermore, the informed consent form states that participants will "sample research cigarettes that may differ in their delivery of tar, nicotine, carbon monoxide, and other tobacco constituents" (p. 1, Summary); that "you will wear a skin patch that may or may not contain nicotine. Whether or not your patch contains nicotine may be determined by chance, like a coin toss." (p. 1, Summary); that "we ask participants to smoke and compare different research cigarettes. These may differ in the amounts of several typical tobacco smoke constituents, such as carbon monoxide, tar, and nicotine." (p. 1, under Purpose); and that "Neither you nor the investigators know if your patch contains nicotine. This is determined by chance. Only the pharmacist handing out the patch will know." (p. 3, second paragraph).
- 6 * Is the research likely to produce psychological discomfort or negative feelings in the participants?
 Yes No
- 6.1 If Yes, describe the arrangements made to provide professional counseling or support resources to any participants requiring such assistance following their participation in the study:
- 7 * Will the participants be required to deceive others?
 Yes No
- 8 * Will the participants be debriefed?
 Yes No
- 8.1 If Yes, describe the debriefing process:
Upon completion of the entire study, participants will be sent a letter (see below) explaining that the critical variable in which the research cigarettes differed from each other was nicotine content and none of the other constituents also listed as possibly differing, and furthermore explaining that the nicotine patch contained nicotine for all study participants, not just some. We cannot debrief each individual participant when they complete the study because they may communicate this information to other potential participants.

Upload a copy of the debriefing script:

Name	Created	Modified Date
Debriefing Letter(0.01)	8/26/2019 4:46 PM	8/26/2019 4:46 PM

- 8.2 If No, justify why the deception will not be disclosed/explained to the participants at the conclusion of the study:
- 9 * Describe the additional training and qualifications of the research staff who are involved in the deception process and the debriefing:
None of the research staff have any additional training or additional qualifications related to deception.

Sample Collection/Analysis

You indicated on the "Type of Research" page that your study involves a sample (specimen) collection and/or analysis.

1 * What type of samples will be involved in this study? (Check all that apply)

Prospective (will be collected)
 Existing (previously collected at the time of initial IRB submission)

2 * Will genetic analysis/testing be done on any of the samples?

Yes No

3 * Will this study involve banking of samples (storing for future research use)?

Yes No

4 * What is the purpose of the sample collection and/or analysis?

Aurine sample will be obtained for drug and pregnancy testing during screening and whenever intoxication is suspected. A blood sample (10 ml) will be obtained from a forearm vein, one time, in those individuals who opt in to the procedure. The blood draw can be performed at any time after the consent form was signed - the participant does not have to pass screening for the main study. The blood will be analyzed for heavy metal and aldehyde concentrations. The purpose is to collect pilot data for a new grant application centered around smoking and psychiatric illness. The samples will be frozen until completion of study procedures, upon which they will be analyzed.

5 * Is there the possibility that cell lines will be developed with any of the samples?

Yes No

6 * Will the samples be released to anyone not listed as an investigator on the protocol?

Yes No

6.1 If Yes, give name(s) and affiliation(s):

The blood sample will be analyzed by Drs. [name] and [name] at the UM School of Pharmacy. Samples will be labeled with the participant code # and no PII. Drs. [name] and [name] will not be able to link samples to PII and are therefore not listed on this protocol.

7 * Will the sample material be sold or given to any third parties?

Yes No

7.1 If Yes, give name(s) and address(es):

Prospective Samples

You indicated that the study involves collection of prospective samples (specimens).

1 * What type of sample will be collected? (Check all that apply)

- Blood**
- Bone Marrow Aspirate/Biopsy
- Cerebrospinal Fluid
- Saliva
- Skin
- Sputum
- Stool
- Tissue
- Tumor
- Urine**
- Other

1.1 If Other, specify:

2 For blood draws, specify the amount drawn, in teaspoons, at each visit and across the course of the subject's entire participation time:

2 teaspoons (10 ml) of venous blood one time, at any one of the study visits.

3 * What type of samples will be collected? (Check all that apply)

- Samples obtained specifically for research purposes-obtained via a separate collection procedure done solely for the purposes of the study**
- Samples obtained specifically for research purposes-additional taken during a clinical procedure
- Leftover samples that were obtained for clinical purposes (no additional research procedures required)
- Commercial (for profit) samples
- Other

3.1 If Other, specify:

4 * How are these samples labeled? For example, do they contain name, initials, dates, Social Security number, medical record number, or other unique code?

Urine samples are not labeled. Drug and pregnancy testing is performed immediately after the sample is obtained. The sample is then discarded.

Blood sample are labeled with the participant's ID code, the date, study number, type of matrix(plasma), and the initials of the person obtaining the sample.

5 * Will sample(s) be made available to the research subject (or his/her medical doctor) for other testing?

Yes No

6 * If a participant withdraws from the study, will that participant have the option to get the remaining portion of their sample(s) back?

Yes No

7 * If the participant withdraws, explain how their sample(s) will be handled (For example, will sample(s) be destroyed, anonymized, etc.):

The urine sample will already have been discarded.

The blood sample will be retained unless the participant asks for it to be destroyed.

8 * Will the samples be destroyed after the study is over?

Yes No

8.1 If No, describe how the samples will be stored, where they will be stored, and for how long.

ID: VIEW4E0E257D60C00
Name: v2_Prospective Samples

Clinical Trial Registration

You indicated on the "Type of Research" page that your study is a **clinical trial**.

1 * Does the UM Clinical Trials Registry policy require registration of this trial?

Yes No

2 * Has this trial been registered?

Yes No

ID: VIEW4E093BF078C00
Name: v2_Clinical Trial Registration

Clinical Trial Registration Information

You indicated that this clinical trial has been registered.

1 * Was this trial registered at www.clinicaltrials.gov?
 Yes No

2 If no, was this trial registered on a site other than clinicaltrials.gov?
 Yes No

2.1 If Yes, specify the name of the other site:

2.2 Provide justification for registering this trial on this site:

3 * Registration Number
NCT04001114

ID: VIEW4E093BF1D0800
Name: v2_Clinical Trial Registration Information

Participant Selection

1 * How many local potential participants (or specimens/charts) do you anticipate will be screened for this study? **Screening includes determining potential participants' initial eligibility for and/or interest in a study.**

160

2 * How many participants (or specimens, or charts) will be enrolled/used for this study? **A local prospective participant is considered enrolled in the study when a UM-approved Informed Consent Document (not including separate screening consent forms) is signed.**

Local - the number being enrolled at this site:

160

Worldwide - the number being enrolled total at all sites (including local enrollment):

160

3 * Gender:

- Male
- Female

4 * Age(s):

- 0 to 27 days (newborn infants)
- 28 days to 12 months (Infant)
- 13 months to 23 months (Toddler)
- 2 to 5 years (Preschool)
- 6 to 11 years (Child)
- 12 to 17 (Adolescents)
- 18 to 88 years (Adult)
- 89 years and older

5 * Race/Ethnicity:

- All Races Included
- American Indian or Alaskan Native
- Asian/Other Asian
- Asian/Vietnamese
- Black or African American
- Hispanic or Latino
- Mixed Race or Ethnicity
- Native Hawaiian or Pacific Islander
- White or Caucasian

6

* Language(s):

- English
- Chinese
- French
- Italian
- Japanese
- Korean
- Local Dialect

- Spanish
- Vietnamese
- Other

